- The duration of response is measured from the time of initial response until documented tumour progression, death, or dropout.

Exploratory outcome measures

- CLEVER-1 on circulating monocytes will be determined by flow cytometry. The proportion of circulating CD14+ monocytes binding labelled FP-1305 prior to treatment and their MFI will be used to define CLEVER-1 positivity. CLEVER-1 in tumour samples (if available) prior to treatment will be identified with immunohistochemistry and reported as positive cells / mm² of sample. The MFI of CLEVER-1 positive cells will be correlated to the number of CLEVER-1 positive cells in the tumour sample if the number is available.
 - Clever-1 anti-FP-1305 MFI
 - Clever-1 anti-9-11 MFI
 - Anti-PD-1 MFI
- Anti-CTLA-4 MFI The proportion of circulating monocytes binding labelled FP-1305 and another CLEVER-1 binding antibody prior to and during the treatment at selected time points and their MFI will be reported.
 - Clever-1 anti-FP-1305 % of cells
 - Clever-1 anti-9-11 % of cells

- S-CLEVER-1 and its blockage will be determined by measuring the amount of S-CLEVER-1 with immunoassay prior to treatment and during the treatment.
- CD8 positive cells within the tumour stroma prior to treatment will be identified with immunohistochemistry and reported as positive cells/mm² of sample. The subjects will be grouped according to response (CR/PR/SD/Progressive disease) and the mean number of CD8 positive cells according to each group will be reported.
 - In addition to CD8, also CD4, CD163 and FoxP3 positive cells have been measured
- Progression free survival as the time from subject allocation into the trial until documented disease progression according to RECIST 1.1 or death will be measured in the population that has been dosed at least once.
- Overall survival is defined as the time from subject allocation into the trial until death from any cause and will be measured in the population that has been dosed at least once. Data will be censored on the last documented data that the subject has been alive.

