Regarding Part II, the first three subjects recruited to the unique cohort are included in the DLT evaluable population. The amount is expanded to six subjects if there is one DLT event in the first three subjects. The following cohorts are investigated: Q3W cohorts at dose levels that have not previously been tested in Part I, Q2W cohorts at each new dose level and Q1W cohorts at each new dose level. DLT assessment period in Part II is 4 weeks from the first dose of FP-1305.

Efficacy evaluable population: Includes all subjects who have received at least one dose of FP-1305 for the first time and has tumour imaging conducted at the baseline, and at least once during the treatment or progress or die due to their disease before the first tumour imaging post FP-1305 administration. This formulates the Full Analysis Set for Efficacy (FAS-E).

In the FAS populations also Part I subjects will be included.

9 General statistical considerations

Summary statistics will include at least the number of subjects, mean, standard deviation, median, minimum and maximum for continuous variables, and frequencies and percentages for categorical variables. All data collected will be listed by subject.

In Part II, the disease group or dosing cohorts of 10 subjects will be presented separately as also the Simon's design rule will be applied separately for each cohort. In addition, the cohorts using originally recommended dosing regimen for Part II, Q3W (1.0 mg for all cohorts and 0.3 mg/kg and 3.0 mg/kg for colorectal adenocarcinoma), will form a population (originally enrolled part II cohorts). Also, a pooled population of Part I subjects (n=30) and Part II originally enrolled subjects (n=120) will be used for survival endpoints. The total number of subjects in this dataset is n=148 as there were 2 part I subjects (colorectal adenocarcinoma 0.3 mg/kg) included in Part II.

In the statistical analyses a p-value less than 0.05 will be considered as an indication of statistical significance. If not stated otherwise, all tests will be performed as two-sided tests and two-sided 95% confidence intervals will be produced. Missing values will not be imputed in the analyses.

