9.3 Examination of subgroups

All analyses will be presented by tumor type cohorts. In addition, within colorectal adenocarcinoma, results will be presented by dose and by dosing frequency. Furthermore, some disease group cohorts can be combined for subgroup analyses:

- disease cohorts in which there are subjects who have at least SD for overall response evaluation
- cutaneous melanoma, cholangiocarcinoma, gastric adenocarcinoma and hepatocellular cancer which have subjects with a long duration of disease control
- cutaneous melanoma, cholangiocarcinoma and gastric adenocarcinoma cohorts (30 subjects) will be used as a subgroup of investigating the possible predictive markers of clinical benefit, in addition to whole subject population

Subgroup presentations to be done will be indicated in the sections below.

10 Demographic and other baseline characteristics

Number of subjects enrolled into the study at screening and the reasons for screening failures will be summarized. The number of subjects entering and completing the study will be summarized. All subjects discontinuing the study will be summarized together with the reason(s) for discontinuation and time of discontinuation (visit/cycle).

Demographic and baseline characteristics will be summarized by disease group using descriptive statistics. Following variables will be analysed.

- Gender
- Age at entry
- Race
- Weight
- Pregnancy test (females of child-bearing potential)
- Tumour information and other baseline disease characteristics

Medical history, prior and concomitant medications/therapies will be presented by frequency and subject count-based tables according to MedDRA/WHO Anatomical Therapeutic Chemical (ATC) classification.

A prior medication is a medication with end date strictly before administration of first dose of IMP.

11 Extent of exposure and compliance

Treatment exposure (number of cycles), study duration and treatment compliance will be summarised for all subjects and by disease group cohorts using descriptive statistics.

12 Outcome variables

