12.1 Primary outcome variables

ORR (CR or PR), CBR (CR, PR or SD) and irORR (irCR or irPR) will be reported as the proportion of subjects of all efficacy evaluable subjects within each tumour type cohort and dosing regimen, both at cycle 4 and at cycle 7. The 90% confidence intervals for ORR, CBR and irORR will be calculated. Results from each tumour type (disease group) will be reported separately. There has been

recent debate about the definition of CBR and DCR. Recent article (“Clinical endpoints in oncology - a primer” by Delgado and Guddati) described that for CBR the SD should last at least 6 months. For clarity, and in order to comply with study protocol the tumour imaging results according the RECIST 1.1 will be presented by cycles (doing so there is no difference in the definition of DCR and CBR). Additionally, we are reporting the duration of SD to capture also that utility.

It should be noted that although the protocol states that irORR should be evaluated, it requires confirmation of irCR or irPR from an additional tumour evaluation carried out at least 4 weeks after irCR or irPR was established. However, due practical limitations in the population of subjects recruited for this study, the additional tumour evaluation could not be carried out on several occasions (only single PR result so far) and for this reason, ancillary information (e.g., no signs of clinical progression) will be reported for patients who continue treatment beyond PD.

When progression occurs, patients can continue treatment if IMP still is judged beneficial for the patient, i.e., clinical status does not indicate progression. This will be summarized using the following categories:

- No evidence of progression
- Evidence of progression, IMP still beneficial
- Evidence of progression, patient withdrawn

This presentation will be done for the first tumor imaging and first time of progression for the DCR subjects. Also, the confirmation image result will be reported for patients continuing IMP beyond progression.

Simon’s Two-Stage design will be used to evaluate efficacy and decide whether the cohort can be further expanded or not for Part III. The expansion of each disease group cohort is based on CBR (at cycle 4 or at cycle 7 for the Q3W dosing regimen) and the required proportion to proceed to Part III is 1/10. The same definition, CBR at cycle 4 or at cycle 7, will be used for the classification of subjects (DCR vs non-DCR) in the analyses.

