12.3 Exploratory outcome variables

The proportion of lymphocyte subsets (CD4, CD8, their ratio, NK-cells, B-cells and regulatory T-cells from CD127 FoxP3 assay) will be analysed at given time points with flow cytometry and plotted against the scheduled sampling time. The level of circulating cytokines and chemokines (these may include but are not limited to the following IFN α , IFN γ , IL-1 α , IL-1 β , IL-1RA, IL-2, IL-4, IL-5, IL-6, IL-7, IL-8/CXCL8, IL-9, IL-10, IL-12p70, IL-13, IL-15, IL-17A, IL-18, IL-21, IL-22, IL-23, IL-27, IL-31, TNF α , TNF β , GM-CSF, Eotaxin/CCL11, GRO alpha/CXCL1, IP-10/CXCL10, MCP-1/CCL2, MIP-1 α /CCL3, MIP-1 β /CCL4, RANTES/CCL5, SDF-1 α /CXCL12) will be analysed by multiplex assays pre- and post-treatment. Aggregated data (mean and median) from each dose level will be presented using descriptive statistics by tumour type cohort.

The change in LDH, LDL and OxLDL, CRP, CA-125 (OC subjects), CA19-9 (PDAC, gallbladder cancer, cholangiocarcinoma, gastric adenocarcinoma subjects), CEA (CRC, ER+ BC, gastric adenocarcinoma subjects), CA-15-3 (ER+ BC subjects) and AFP (HCC subjects) levels in the subjects pre- and post-treatment will be reported with descriptive statistics.

The immune cell profile, the level of circulating cytokines and chemokines, CLEVER-1 on circulating monocytes, IHC parameters (CD4 positive cells, CD8 positive cells, CD163 positive cells and FoxP3 positive cells), Clever-1 and PD-L1 staining parameters (intra-tumoral VCs/Positive viable cells/Combined positive score for STAB1, and Combined positive score for PD-L1) and possible genetic analyses during the first four cycles of treatment will be reported using descriptive statistics (by DCR and non-DCR, and in total) and visualizations. If feasible, exploratory statistical analyses will also be used to describe the associations.

Overall survival data, including but not limited to the six-month, one-year and two-year survival rates will be reported for each cohort, and will be analyzed using the Kaplan-Meier method and Cox-modelling where appropriate.

Progression free survival including but not limited to the six-month, one-year and two-year survival rates will be reported for each tumor type cohort and will be analyzed using the Kaplan-Meier method and Cox-modelling where appropriate.

Duration of response (CR, PR or SD) will be reported using descriptive statistics.

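### SAP Part II ends duration of response and stable disease at dropout and summarises it by plain mean and median, so durations cut short count as complete; the start for stable disease is left ambiguous

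*SAP*

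**What the plan says.** The secondary outcome measures in SAP Part II section 5 define the endpoint: "The duration of response is measured from the time of initial response until documented tumour progression, death, or dropout". Section 12.3 widens it and names the method: "Duration of response (CR, PR or SD) will be reported using descriptive statistics". Section 9 says what that means: "Summary statistics will include at least the number of subjects, mean, standard deviation, median, minimum and maximum for continuous variables".

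Other time-to-event outcomes in the same SAP are handled differently. For overall survival, section 5 adds: "Data will be censored on the last documented data that the subject has been alive". Section 12.3 names Kaplan-Meier and Cox models for overall and progression-free survival. The table and figure plan (20.1) has Kaplan-Meier entries for those two and one plain duration-of-response table. Section 9.1 says only that missing values are not imputed.

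On SD, section 12.1 mentions an article that asks for SD to last at least 6 months, keeps the protocol definition of clinical benefit, and continues: "Additionally, we are reporting the duration of SD to capture also that utility". Section 9.3 allows cohorts to be combined, one group being "cutaneous melanoma, cholangiocarcinoma, gastric adenocarcinoma and hepatocellular cancer which have subjects with a long duration of disease control".

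The protocol repeats the definition (synopsis, 3.10, 15.3.3) and adds neither a censoring rule nor an SD start.

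**The concern.** Progression and death end disease control. Dropout ends only the observation of it. A plain mean or median cannot tell the two apart, so a subject who leaves while still controlled contributes a shortened value as if it were final. Such cases are foreseen: the protocol's RECIST appendix provides for subjects who stop because of general deterioration without objective progression.

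The start of the clock adds a second uncertainty. For a subject whose best result is SD, the initial response is presumably the first scan showing SD, since section 12.3 counts SD among the responses. The SAP does not write this down, and a programmer could count from first dose.

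At stake is a named secondary outcome of Part II. SD duration is also the SAP's answer to the cited 6-month criterion, and four cohorts are already described by long disease control, with no written rule a reader could check that against.

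**Working it through.** The plan states no figure for this endpoint, so there is none to reproduce.

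**Inputs from the documents.** Cycles last 21 days (protocol 8.3). Scans fall at Cycles 1, 4, 7, 10 and every third cycle up to one year (protocol 8.4.2). The scan interval is therefore 63 days, D = 63/30.44 = 2.07 months, and the first on-treatment scan comes 9 weeks after first dose.

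**Assumptions.** SD is seen at Cycle 4. Residual time to progression is exponential with median 4 months, so L = ln 2/4 = 0.1733 per month, and progression is documented at the next 9-week scan. Dropout is exponential and independent of progression, with rate m = L·d/(1−d) for d = 0.10, 0.25, 0.40. The 9-week grid runs indefinitely.

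**Formulas.** Let q = exp(−LD) = 0.699 and r = exp(−mD), the chances of passing one interval without progression and without dropout.
- True mean from the Cycle 4 scan: D/(1−q) = 2.07/0.301 = 6.87 months. From first dose, add D: 8.94.
- Planned mean from the Cycle 4 scan: [(1−r)/m]/(1−qr).
- Share of durations ending in dropout: (1−r)/(1−qr).

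| d | m | r | Share ending in dropout | Planned mean from Cycle 4 scan | Error | Planned mean from first dose | Error |
|---|---|---|---|---|---|---|---|
| 0.10 | 0.0193 | 0.961 | 12% | 6.17 | −10% | 8.24 | −8% |
| 0.25 | 0.0578 | 0.887 | 30% | 5.13 | −25% | 7.20 | −19% |
| 0.40 | 0.1155 | 0.787 | 47% | 4.09 | −40% | 6.16 | −31% |

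**Median.** The true median from the Cycle 4 scan is two intervals, 4.14 months, because q = 0.699 and q² = 0.488. The share still observed just before that second scan is q·r² = 0.645, 0.550 and 0.433. In the first two cases it is above one half, so the planned median is also 4.14. In the third it crosses one half when q·exp(−mt) = 0.5, at t = 2.90 months. The error is 0, 0 and −30%; from first dose (4.97 against 6.21) it is 0, 0 and −20%.

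**If every dropout is really a failure.** The planned mean is then the correct one, and censoring at dropout returns the larger value. Counted from the Cycle 4 scan, the censored mean is too long by 6.87/6.17, 6.87/5.13 and 6.87/4.09, that is 11, 34 and 68%. From first dose the excess is about 8, 24 and 45%.

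**SD start.** SD at Cycle 4 with progression documented at Cycle 10 lasts 9 × 21 = 189 days (27 weeks, 6.2 months) from first dose and 6 × 21 = 126 days (18 weeks, 4.1 months) from the SD scan. The same subject is above 6 months on one start and below it on the other.

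**The case against.** Several points count against making much of this.

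- **Status.** SAP section 16 calls its analyses exploratory. Expansion depends on clinical benefit at Cycle 4 or 7, not on duration. This stands and limits the weight of the point.
- **Existing output.** Section 9 promises: "All data collected will be listed by subject". Responses are shown by cycle, reasons for and timing of discontinuation are summarised, and progression-free survival gets Kaplan-Meier. A reader can find the dropouts, but listings do not correct the summary table. Progression-free survival covers all dosed subjects from allocation, so it is not duration among controlled subjects.
- **Few ongoing cases.** SAP section 2 says the originally enrolled cohorts have finished treatment. This limits durations still running at the lock, not dropout.
- **Unknown direction.** Deterioration without documented progression is probably informative. Censoring would then overstate duration, which is why a sensitivity analysis is needed. In the base case the planned median is unaffected at 12% and 30% dropout.
- **Scan grid.** Nine-week imaging stops at one year, and after that only the 18- and 24-month images are mandatory. On that sparser grid the mean errors from the Cycle 4 scan are about −12, −28 and −45%, so the base case does not exaggerate the mean error.

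A reader might also infer that SD has no start at all. The documents do not support that: sections 5 and 12.3 together point to the first SD scan, so the start is ambiguous, not absent. Nor do they support the inference that a planned 6-month SD rate is compromised, since neither section 12.1 nor the table plan includes one.

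**Conclusion.** The point holds as a gap in the analysis rule for a secondary, exploratory endpoint. The SAP lists dropout as an end of duration and plans only summaries that cannot use censoring, so durations cut short are counted as complete. The SD start needs one written sentence, because the two possible starts differ by about 9 weeks.

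The size is illustrative. It assumes exponential times, a 4-month residual median, dropout unrelated to progression, and 9-week scans throughout. Under those assumptions the loss in the mean runs from 8 to 40% across both starts and the three dropout shares. The median is affected only at the highest share, by 20 or 30%.

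It would go too far to say that the plan certainly understates duration. That depends on why subjects drop out, and the documents give neither a rate nor reasons. At the other extreme, where all dropouts are failures, the planned summary is right.

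**What to change.** Amend SAP Part II sections 5 and 12.3, and carry the same rules into the Part III SAP, because protocol 3.10 gives Part III the same definition.

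1. Define documented progression and death as the events.
2. Censor dropout without progression, and control still ongoing at the lock, at the last evaluable tumour assessment.
3. State one start date for SD and one for CR/PR.
4. Report the numbers of events and of censored subjects.
5. Give Kaplan-Meier estimates of CR/PR/SD duration in the population that section 9 already sets up: "a pooled population of Part I subjects (n=30) and Part II originally enrolled subjects (n=120) will be used for survival endpoints" (148 subjects after removing the 2 counted in both parts). Add a sensitivity analysis that counts dropout as an event.
6. For CR/PR (a single PR so far, by section 12.1) and for single 10-subject cohorts, replace the plain mean with individual durations flagged as progression, death, dropout or ongoing.

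The cost is SAP wording and a little more analysis, since Kaplan-Meier and the pooled population are already planned. The downside is imprecision in small groups. In simulation under the assumptions above (d = 0.10, 0.25, 0.40), the upper 95% limit of the median is never reached with 3 or 5 controlled subjects. With 10 it is not reached in 23, 63 and 88% of cases, and with 30 in 0, 1 and 18%. This is why item 6 does not ask for curves in single cohorts.

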9.1 Handling of dropouts or missing data

Missing values will not be imputed.

9.2 Interim analyses and data monitoring

The study has no predefined interim analysis. Interim analyses on safety and efficacy or on PK, immunogenicity, and selected biomarkers may be provided on ongoing basis prior to completion of the trial in order to expedite conclusions and to support trial presentations or publications.

Currently, the study data has been presented for Part I (n=30, reported under separate SAP), and for the Part II population of fully enrolled cohorts (in August 2021 for ESMO and ASCO congresses, all other disease group cohorts than anaplastic thyroid cancer, n=110). Also, a pooled population of Part I and these Part II fully enrolled cohorts (n=138, as there were 2 part I colorectal adenocarcinoma 0.3 mg/kg subjects included in Part II) was used in these presentations.

9.3 Examination of subgroups

All analyses will be presented by tumor type cohorts. In addition, within colorectal adenocarcinoma, results will be presented by dose and by dosing frequency. Furthermore, some disease group cohorts can be combined for subgroup analyses:

- disease cohorts in which there are subjects who have at least SD for overall response evaluation
- cutaneous melanoma, cholangiocarcinoma, gastric adenocarcinoma and hepatocellular cancer which have subjects with a long duration of disease control
- cutaneous melanoma, cholangiocarcinoma and gastric adenocarcinoma cohorts (30 subjects) will be used as a subgroup of investigating the possible predictive markers of clinical benefit, in addition to whole subject population

Subgroup presentations to be done will be indicated in the sections below.

10 Demographic and other baseline characteristics

Number of subjects enrolled into the study at screening and the reasons for screening failures will be summarized. The number of subjects entering and completing the study will be summarized. All subjects discontinuing the study will be summarized together with the reason(s) for discontinuation and time of discontinuation (visit/cycle).

Demographic and baseline characteristics will be summarized by disease group using descriptive statistics. Following variables will be analysed.

- Gender
- Age at entry
- Race
- Weight
- Pregnancy test (females of child-bearing potential)
- Tumour information and other baseline disease characteristics

Medical history, prior and concomitant medications/therapies will be presented by frequency and subject count-based tables according to MedDRA/WHO Anatomical Therapeutic Chemical (ATC) classification.

A prior medication is a medication with end date strictly before administration of first dose of IMP.

11 Extent of exposure and compliance

Treatment exposure (number of cycles), study duration and treatment compliance will be summarised for all subjects and by disease group cohorts using descriptive statistics.

12 Outcome variables

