PPS	Per protocol set
irPR	Immune-related Partial response
PR	Partial response
RECIST	Response Evaluation Criteria In Solid Tumors
SD	Stable disease

SAE	Serious adverse event
TEAE	Treatment emergent adverse event

2 General remark

This is a statistical analysis plan (SAP) for the Part II of the trial. For Part I, there were separate SAP's for the dose escalation part conducted with TITE-CRM methodology (finalized March 29th 2019) and for the all other remaining variables (finalized March 26th 2020). This SAP version is created at the time when for the originally enrolled Part II cohorts have finished their treatment and these subjects' data (12 cohorts of ten subjects, n=120) will be reported and compiled for TLF package. For some purposes, also the part I subjects' data (n=30) will be used to analyze the full cumulative data of the study so far.

Since the study still is ongoing a so-called soft lock of the study data will be made. It should be noted that protocol deviations will not be locked at this time.

3 Study objective(s) for Part II

Primary Objective for Part II

- To determine the safety, tolerability and preliminary efficacy of FP-1305 monotherapy with the ORR, CBR and irORR in distinct expansion groups of subjects with advanced (inoperable or metastatic) solid tumours of the selected tumour types

Secondary Objectives for Part II

- To determine CLEVER-1 positivity in each tumour type
- To characterize the PK profile of a single dose of FP-1305 after the first dosing for each cohort of different tumour type
- To characterize the PK profile of FP-1305 during repeated dosing in each cohort of different tumour type
- To assess the host immune response to FP-1305 (immunogenicity) in each tumour type
- To explore potential predictive markers associated with FP-1305 clinical activity as determined by ORR, CBR and irORR
- To investigate the duration of response in the subject group that has a complete or partial response, or SD

Exploratory Objectives for Part II

- To assess the amount of soluble CLEVER-1 (S-CLEVER-1) in the subjects prior to treatment
- To characterize the receptor occupancy of FP-1305 on S-CLEVER-1 and/or on circulating monocytes at different dose levels/dosing frequencies
- To assess the CBR of trial subjects according to the number of CD8 positive cells within the tumour stroma
- To assess progression free survival in trial subjects who receive at least 1 dose of FP-1305

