20.1 Table and figure plan

List of planned tables:

Section 14.1
Disposition of subjects
Demographics and baseline characteristics
Medical history
Prior medications
Concomitant medications - other than chemotherapy or concomitant procedures
Concomitant medications related to chemotherapy or concomitant procedures
Extent of exposure and compliance
Section 14.2.1
Best response at any timepoint for Target-lesion, non-Target lesion and Overall response
Response by cycle
Simon's two-stage evaluation of stage one
Other response related information
Section 14.2.2
Monocytes CLEVER-1 positivity
S-CLEVER-1 and its occupancy by FP-1305
Serum concentration of FP-1305
Anti-human FP-1305 antibodies
Section 14.2.3
Lymphocyte subsets
B-cells

Regulatory T-cells
Circulating cytokines and chemokines
Change in LDH, LDL, CRP
Change in OxLDL
Change in CA-125
Change in CA19-9
Change in CEA
Change in CA-15-3
Change in AFP
Response with the immune cell profile by DCR and in total
The level of circulating cytokines and chemokines by DCR and in total
CLEVER-1 on circulating monocytes by DCR and in total
IHC parameters
Clever-1 and PD-L1 staining parameters
Overall survival
Overall survival (Cox regression)
Overall survival (Kaplan-Meier)
Progression free survival
Progression free survival (Cox regression)
Progression free survival (Kaplan-Meier)
Duration of response
Association of tumor responses to survival (Landmark analysis)
Length of latest prior treatment line for the cancer impact on survival
Length of latest prior treatment line compared to length of treatment in study
Subgroup evaluations
ECOG
Section 14.3.1
Overall summary of TEAEs
TEAEs by system organ class and preferred term
TEAEs by system organ class and preferred term by causality
TEAEs by system organ class and preferred term by severity
Serious TEAEs by system organ class and preferred term
TEAEs leading to discontinuation of study drug by system organ class and preferred term
Overall summary of pooled (Part 1 and Part 2) TEAEs by dose
Section 14.3.3
Hematology
Hematology shift
Chemistry
Chemistry shift
Urinalysis
Other lab parameters

Section 14.3.3

Vital signs
ECG
ECG maximum change
ECG abnormal findings
Physical examination

List of planned figures:

Section 14.2.4

Serum concentration of FP-1305
Lymphocyte subsets
B-cells
Regulatory T-cells
Macrophage HLA expression
Myeloid derived suppressor cell populations in circulation
Immune cell profile by DCR status and overall

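### Part II SAP section 9.3 allows tumour cohorts to be pooled by their observed disease control, without restricting what is estimated in those pools; any efficacy or survival estimate there would be biased upward

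*SAP*

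**What the plan says.** The Part II SAP, section 9.3 (Examination of subgroups), presents all analyses by tumour type cohort and then adds that "some disease group cohorts can be combined for subgroup analyses". Three combinations follow:

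- **First pool:** "disease cohorts in which there are subjects who have at least SD for overall response evaluation".
- **Second pool:** "cutaneous melanoma, cholangiocarcinoma, gastric adenocarcinoma and hepatocellular cancer which have subjects with a long duration of disease control".
- **Third pool:** "cutaneous melanoma, cholangiocarcinoma and gastric adenocarcinoma cohorts (30 subjects) will be used as a subgroup of investigating the possible predictive markers of clinical benefit", alongside the whole subject population.

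Section 9.3 says that later sections will show which subgroup presentations are to be made. Sections 10 to 16 name none. The table plan in 20.1 has a single entry, "Subgroup evaluations", placed among the exploratory tables.

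On timing, section 2 (General remark) states: "This SAP version is created at the time when for the originally enrolled Part II cohorts have finished their treatment". Section 9.2 records that results had already been presented "in August 2021 for ESMO and ASCO congresses, all other disease group cohorts than anaplastic thyroid cancer, n=110".

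Section 12.1 defines CBR as CR, PR or SD and treats it as a primary outcome. Section 9 treats p below 0.05 as statistically significant and produces two-sided 95% confidence intervals unless stated otherwise. Section 16 calls the analyses exploratory.

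**The concern.** A cohort enters the first pool by having at least one subject with SD or better, and that is the event CBR counts. A cohort enters the second pool because some of its subjects were observed to have long disease control. In both cases the sample is chosen by the quantity that an efficacy summary would then estimate. Cohorts of 10 vary widely by chance. Dropping those that happened to have no benefit leaves a pool that looks more active than the tumour types in it really are, even if all types share one rate.

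Duration of disease control, PFS and OS are affected as far as they correlate with the selecting outcome. Section 9.2 allows results to be released during the trial for presentations and publications. A pooled rate could therefore circulate without the rule that produced it.

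**Working it through.** **The plan's own figure.** The documents give no figure for the pools. The related stated figure is the Simon design in protocol 15.7: 5% against 20%, one-sided alpha 0.05, power 0.80, continue with at least 1 of 10, succeed with at least 4 of 29. An exact two-stage binomial sum gives alpha 0.0468 and power 0.801. The design reproduces, and its error rate already allows for the stage-one selection.

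**First pool: inputs.** There are 12 cohorts of 10, n=120 (Part II SAP, section 2). Entry requires at least one subject with SD or better, taken here as at least 1 of 10 with clinical benefit. The true CBR, p, is not given, so a range is shown. Assumptions: one common p and independent subjects.

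**Formula.** The probability that a cohort is selected is s = 1 − (1 − p)^10. The expected CBR among selected cohorts is p / s.

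| True CBR | s | Cohorts selected (12 × s) | Expected CBR in pool | Excess, points |
|---|---|---|---|---|
| 5% | 0.4013 | 4.8 | 0.05 / 0.4013 = 12.5% | 7.5 |
| 10% | 0.6513 | 7.8 | 0.10 / 0.6513 = 15.4% | 5.4 |
| 20% | 0.8926 | 10.7 | 0.20 / 0.8926 = 22.4% | 2.4 |
| 30% | 0.9718 | 11.7 | 0.30 / 0.9718 = 30.9% | 0.9 |
| 40% | 0.9940 | 11.9 | 0.40 / 0.9940 = 40.2% | 0.2 |

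Simulation of 10 and of 12 cohorts with a common rate agrees at 5% to 30%.

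**Colorectal counted once.** Section 9.3 speaks of disease cohorts, and the three colorectal dose groups could count as one cohort of 30. There are then nine cohorts of 10 and one of 30. Expected responders divided by expected subjects in the pool is 120p / [90(1 − (1 − p)^10) + 30(1 − (1 − p)^30)]:

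- p = 5%: 6 / 59.67 = 10.1%
- p = 10%: 12 / 87.35 = 13.7%
- p = 20%: 24 / 110.3 = 21.8%

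**Second pool.** No threshold is given for long disease control, so the bias cannot be computed. As an illustration only, take 10 cohorts of 10 with identical exponential durations and keep the four cohorts with the longest single duration. Mean duration in the kept cohorts is 22% above the truth (1.22 against 1.00). The share of subjects lasting beyond twice the true median is 30.6% against 25.0%.

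**The case against.** The strongest reply is that the SAP never says efficacy will be estimated in the first two pools. Pooling is optional. Section 12.1 reports ORR, CBR and irORR by tumour cohort and dosing regimen, and section 12.3 reports PFS and OS by cohort. The only stated use of a pool is marker work in the third. All of that is correct, so a reader should not infer that the plan commits to headline rates in the selected pools. What stands is that the plan sets outcome-based pooling rules, lists a subgroup output, promises details that do not appear, and restricts nothing.

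A reader might also infer that the selection contaminates the choice of tumour types for Part III. The documents do not support this. The Simon rule is applied cohort by cohort, no decision uses the pools, and Part III enrols further subjects.

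Larger inflation figures come from keeping the best three or four of ten cohorts ranked by CBR: 34% and 31% at a true 20%. No pool in the SAP uses that rule, so those figures should not be attributed to it.

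The third pool is three of the four tumour types in the second, but it is a set for marker analysis. A raised response rate does not translate directly into a biased marker association, so the inflation argument does not carry over to that use.

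The exploratory label is fair context. It does not remove the bias from a reported estimate.

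**Conclusion.** The point holds as a gap in section 9.3. Two permitted pools are defined by observed outcome after the data were available, their endpoints are unspecified, and no caveat is attached. Any CBR, duration of disease control, PFS or OS estimate in them would be biased upward.

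For the first pool the excess in CBR depends strongly on the unknown true rate. It is 7.5 points (2.5-fold) at the protocol's 5% null, 2.4 points at 20%, and under 1 point from 30% upward. It is smaller if colorectal counts as one cohort. These figures assume a common rate; real differences between tumour types would reduce the bias without removing it. For the second pool the direction is clear and the size is not determinable.

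The conclusion goes no further than estimates made in these two pools. Per-cohort estimates, the expansion decision and Part III stand.

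**What to change.** In section 9.3, state that the first two pools will not be used for efficacy or survival estimates, confidence intervals, Kaplan-Meier curves or p-values. For those purposes, point to results already planned: the per-cohort presentations, the pooled originally enrolled Part II population (n=120), and the combined Part I and Part II set (n=148) for survival endpoints.

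If either pool is shown at all, label it as selected on outcome, show it descriptively beside the all-cohort result, and draw no efficacy inference from it. Spell out in 20.1 what the subgroup entry contains. A shrinkage model across cohorts would help to separate real differences from chance but is optional.

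The cost is a few sentences in the SAP. The downside is that the selected pools can no longer supply efficacy rates.
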